4.1.2. Part 2 Monotherapy Dose Expansion

Upon identification of the RP2D(s), up to 5 expansion cohorts will enroll subjects to further determine safety, tolerability, efficacy, PK, and PD of the selected dose(s) as follows:

- **TGA Expansion Cohort A1:** At least 5 and up to approximately 15 subjects with AML will be enrolled and treated at the RP2D identified in Part 1 TGA.
- **TGA Expansion Cohort A2:** At least 5 and up to approximately 15 subjects with MDS/MPN (including aCML, CMML, MDS/MPN-U, and RARS-T) will be enrolled and treated at the RP2D identified in Part 1 TGA.
- **TGA Expansion Cohort A3:** At least 5 and up to approximately 15 subjects with MF will be enrolled and treated at the RP2D identified in Part 1 TGA.
- **TGB Expansion Cohort B1:** At least 5 and up to approximately 15 subjects with MM will be enrolled and treated at the RP2D identified in Part 1 TGB.
- **TGB Expansion Cohort B2:** At least 5 and up to approximately 15 subjects with DLBCL will be enrolled and treated at the RP2D identified in Part 1 TGB.

[figure not shown]
Individual dose titration will be permitted according to Protocol-defined safety parameters. Subjects will continue to receive INCB053914 in 21-day cycles until withdrawal criteria are met.

Part 2 will also include a food-effect study. At least 12 and up to 18 subjects across all expansion cohorts who are able to participate in the food study will have additional PK assessments on Cycle 2 Day 1 and Cycle 2 Day 2, as per Section 7.8.4.

CONFIDENTIAL

CONFIDENTIAL

Figure 2: Combination Therapy Study Design

CONFIDENTIAL

CONFIDENTIAL

4.1.3. Part 3 Combination Therapy Dose-Finding

Part 3 (combination dose-finding) will comprise up to 3 disease-specific treatment groups (Combination Treatment Groups A through C [C-TGA – C-TGC]) and will determine the MTD and/or a tolerated PAD of INCB053914 in combination with 3 SOC agents. The combination dose-finding will use a 3 + 3 design to identify an optimal dose regimen in up to 3 different combination expansion cohorts.

- **Combination Treatment Group A (C-TGA):** INCB053914 + cytarabine in subjects with relapsed/refractory AML.
- **Combination Treatment Group B (C-TGB):** INCB053914 + azacitidine in subjects with relapsed/refractory AML or elderly subjects (≥ 65 years) with newly diagnosed AML (*de novo* or secondary) who are unfit to receive intensive chemotherapy.
- **Combination Treatment Group C (C-TGC):** INCB053914 + ruxolitinib in subjects with primary or secondary MF (PPV-MF or PET-MF) who are currently experiencing a suboptimal response on ruxolitinib monotherapy, defined as follows:
 - Palpable spleen of > 10 cm below the left subcostal margin on physical examination at the screening visit OR
 - Palpable splenomegaly of 5 to 10 cm below left subcostal margin on physical exam AND active symptoms of MF at the screening visit as demonstrated by presence of 1 symptom score ≥ 5 or 2 symptom scores ≥ 3 using the Screening Symptom Form ([Appendix O](#)).

4.1.3.1. Standard-of-Care Agent Combination Cohort Dose-Finding Strategy

Between 3 and up to approximately 10 subjects will be enrolled into cohorts under each of the SOC treatment groups, C-TGA, C-TGB, and C-TGC, as described above. Dose-finding for C-TGA, C-TGB, and C-TGC will proceed independently, with each treatment group following a 3 + 3 cohort design. At least 3 subjects will be enrolled and treated at each dose level. If no DLTs are observed in the initial 3 subjects, the next cohort will begin enrollment at the next higher dose level of INCB053914. If 1 DLT is observed in the first 3 subjects, 3 additional subjects will be enrolled in that cohort. If a DLT occurs in one-third or more of the total cohort (ie, ≥ 2 of 6 subjects), then the MTD will be deemed to have been exceeded, and the next lower dose level will be deemed to be the MTD. Thus, the MTD will be defined as 1 INCB053914 dose level below that at which one-third or more of subjects in a particular cohort report DLTs. If the first cohort exceeds the MTD, a dose de-escalation of INCB053914 will be considered.

A conventional regimen of the SOC agents will be used in all dose-finding cohorts within a given SOC combination treatment group and will remain fixed throughout the dose-finding portion of the study.

The starting dose of INCB053914 in the combination treatment groups will be a PAD and 1 dose level below the highest tolerated dose of INCB053914 monotherapy identified in Part 1 of this study. At the current data cutoff date, the highest tolerated dose of INCB053914 monotherapy was 80 mg BID, which also met the criteria of protocol-defined PAD; thus, the planned starting dose for Part 3 will be 65 mg BID (Dose Level 1 dose). The INCB053914 dose used in Part 3

CONFIDENTIAL

CONFIDENTIAL

will never exceed the monotherapy MTD dose to be identified in Part 1 of the study. [Table 1](#), [Table 2](#), and [Table 3](#) summarize the planned starting doses to be used in the SOC combination dose-finding cohorts. An alternative starting dose and/or subsequent INCB053914 doses (Dose Level 1, 2, and/or 3) may be selected pending emerging safety, PK, and PD data in Part 1.

The sponsor, in consultation with participating investigators, may implement alternate INCB053914 administration, such as intermediate doses, alternate dose regimens, or alternate formulations, depending on emerging PK, PD, and safety results. Each subject will be observed for 1 cycle to be evaluable to assess safety and tolerability of the assigned INCB053914 dose in combination with the chosen SOC regimen. The sponsor, in consultation with participating investigators, may elect to expand a dose cohort(s) deemed tolerable, to up to 12 subjects, in order to obtain supplemental PK, PD, and safety data. The INCB053914 RP2D of the combination treatment group will be selected based on the totality of the data within each treatment group for further investigation in the expansion cohorts, and it is possible that the RP2D could be different among disease types.

Table 1: Planned C-TGA Combination Dose-Finding Cohorts

Dose Level	I-DAC dose	INCB053914 Dose ^a
-1	1 g/m ² ; given as 2-hour infusion on Days 1-5	50 mg BID
1 (starting dose)	1 g/m²; given as 2-hour infusion on Days 1-5	65 mg BID
2	1 g/m ² ; given as 2-hour infusion on Days 1-5	80 mg BID
3	1 g/m ² ; given as 2-hour infusion on Days 1-5	100 mg BID

^a INCB053914 starting dose and subsequent cohort doses may change based on emerging Part 1 safety, PK, and PD data.

Table 2: Planned C-TGB Combination Dose-Finding Cohorts

Dose Level	Azacitidine Dose	INCB053914 Dose ^a
-1	75 mg/m ² SC or IV; given on Days 1-5 and 8-9 of a 28-day cycle	50 mg BID
1 (starting dose)	75 mg/m² SC or IV; given on Days 1-5 and 8-9 of a 28-day cycle	65 mg BID
2	75 mg/m ² SC or IV; given on Days 1-5 and 8-9 of a 28-day cycle	80 mg BID
3	75 mg/m ² SC or IV; given on Days 1-5 and 8-9 of a 28-day cycle	100 mg BID

IV = intravenously; SC = subcutaneously.

^a INCB053914 starting dose and subsequent cohort doses may change based on emerging Part 1 safety, PK, and PD data.

Table 3: Planned C-TGC Dose-Finding Cohorts

Dose Level	Ruxolitinib Dose	INCB053914 Dose ^a
-1	Subject's current stable dose (between 5 mg BID and 25 mg BID)	50 mg BID
1 (starting dose)	Subject's current stable dose (between 5 mg BID and 25 mg BID)	65 mg BID
2	Subject's current stable dose (between 5 mg BID and 25 mg BID)	80 mg BID
3	Subject's current stable dose (between 5 mg BID and 25 mg BID)	100 mg BID

^a INCB053914 starting dose and subsequent cohort doses may change based on emerging Part 1 safety, PK, and PD data.

See Sections 5.1.4, 5.1.5, and 5.1.6 for information on the specific dose regimens for cytarabine, azacitidine, and ruxolitinib, respectively.

CONFIDENTIAL

CONFIDENTIAL

4.1.4. Part 4 Combination Expansion Cohorts

Upon identification of the RP2D combination regimens in the combination dose-finding treatment groups, up to 4 expansion cohorts will enroll to further determine safety, tolerability, efficacy, PK, and PD in the subject populations. The 2 AML expansion cohorts will use a Simon 2-stage design to evaluate the efficacy of the combination regimens.

- **C-TGA Expansion Cohort 1 (C-TGA E1)** will enroll subjects with relapsed/refractory (r/r) AML who will be treated with INCB053914 in combination with I-DAC using the regimen identified from the Part 3 dose-finding. This cohort will use a Simon 2-stage design, details of which can be referenced in Section 9.2.4. If an insufficient number of responders are observed in the cohort at Stage 1, further enrollment in the cohort will be terminated.
- **C-TGB Expansion Cohort 1 (C-TGB E1)** will enroll subjects with newly diagnosed AML (*de novo* or secondary) who are ≥ 65 years at screening and unfit to receive intensive chemotherapy and who will be treated with INCB053914 in combination with azacitidine using the regimen identified from the Part 3 dose-finding. This cohort will use a Simon 2-stage design, details of which can be referenced in Section 9.2.4. If an insufficient number of responders are observed in the cohort at Stage 1, further enrollment in the cohort will be terminated.
- **C-TGC Expansion Cohort 1 (C-TGC E1)** will enroll up to 16 subjects with PMF or secondary MF (PPV-MF or PET-MF) who are currently experiencing a suboptimal response on ruxolitinib monotherapy and who will be treated with INCB053914 in combination with ruxolitinib using the dose identified from the Part 3 dose-finding.
- **Optional C-TGA Expansion Cohort 2 (C-TGA E2)**
If the Part 3 C-TGB dose-finding does not yield a tolerable combination of INCB053914 and azacitidine, or if the Part 4 C-TGB E1 Simon Stage 1 does not yield favorable efficacy data, then the sponsor may elect to evaluate INCB053914 in combination with a L-DAC regimen in this population. This option will use an INCB053914 dose deemed tolerable in combination with I-DAC and will reference safety and tolerability data obtained from the Part 3 C-TGA dose-finding. If the sponsor and investigators believe that the optimal dose regimen of INCB053914 in combination with L-DAC will be different from that of INCB053914 in combination with I-DAC, a separate dose-finding cohort will be initiated to identify the optimal dose regimen of INCB053914 in combination with L-DAC.

4.2. Measures Taken to Avoid Bias

This is an open-label study; no comparisons will be made between subjects or against historical controls. Measurements of safety and efficacy are objective measurements, and only comparisons to pretreatment conditions will be made.

CONFIDENTIAL

CONFIDENTIAL

4.3. Number of Subjects

4.3.1. Planned Number of Subjects

Approximately 3 to 30 subjects per treatment group may be enrolled in Part 1 of the study, and up to 75 subjects may be enrolled in Part 2. In Part 3, approximately 3 to 10 subjects will be enrolled per treatment group, and in Part 4, up to 102 subjects may be enrolled.

4.3.2. Replacement of Subjects

In Part 1 and Part 3, if a subject is not evaluable (eg, at least 80% of the prescribed study drug and SOC agent doses during the first cycle are not taken due to dose interruption, reduction, or discontinuation), another subject will be enrolled at this dose level. Subjects who report DLTs will be considered evaluable for the purpose of determining the safety and tolerability of the dose.

4.4. Duration of Treatment and Subject Participation

After signing the ICF, screening assessments may be completed over a period of up to 28 days. Each subject enrolled in the study may continue to receive study treatment in continuous 21- or 28-day cycles depending upon the treatment regimen. If the subject discontinues all study treatment, the subject will enter follow-up (see Section 6.4). Subjects may continue on study until withdrawal criteria are met. Treatment duration will vary significantly between subjects but is expected to average approximately 4 to 6 months.

4.5. Overall Study Duration

The study begins when the first subject signs the informed consent. The end of the study will occur when all subjects have discontinued study drug and have completed the safety follow-up visit; the sponsor may elect to continue to monitor survival outcome and subsequent therapies for subjects enrolled in Parts 2 and 4. The overall study duration is expected to be approximately 42 months.

4.6. Study Termination

The investigator retains the right to terminate study participation at any time, according to the terms specified in the study contract. The investigator is to notify the IRB/IEC in writing of the study's completion or early termination, and send a copy of the notification to the sponsor or sponsor's designee and retain 1 copy for the site study regulatory file.

The sponsor may terminate the study electively or if required by regulatory decision. If the study is terminated prematurely, the sponsor will notify the investigators, the IRBs and IECs, and regulatory bodies of the decision and reason for termination of the study.

CONFIDENTIAL

CONFIDENTIAL

5. TREATMENT

5.1. Study Drug and Treatment Assignment

5.1.1. Subject Numbering and Treatment Assignment

Upon screening a subject, study sites will contact the IRT in order to receive a subject number.

All subject numbers will be 6 digits; the first 3 digits will be the site number and the last 3 digits will be the subject's number. This subject number will be maintained throughout the study and will not be reassigned. Subjects who fail screening, withdraw consent, or discontinue from the study after being assigned a subject number will retain their initial number.

Upon enrolling the subject, the site staff will contact the IRT to register the quantity of study drug allocated at the initial visit and all subsequent visits at which study drug is dispensed. Refer to the IRT manual for detailed information.

5.1.2. Randomization and Blinding

Not applicable.

5.1.3. INCB053914

5.1.3.1. Description and Administration

INCB053914 drug product is formulated as immediate release (IR) tablets.

INCB053914 will be self-administered orally BID beginning with the Cycle 1 Day 1 morning dose and continuously thereafter in 21- or 28-day cycles, or appropriate visit intervals, depending on the treatment group regimen until treatment withdrawal criteria are met. Exceptions are noted in the Schedule of Assessment tables ([Table 6](#), [Table 9](#), [Table 12](#), [Table 15](#), [Table 18](#)), when the morning dose will be administered in the clinic to accommodate PK sample collection. Dose increases will be accomplished using the following options: 1) increasing the number of tablets taken at each QD administration, or 2) increasing administration frequency to BID, or 3) increasing the number of tablets taken at 1 or more dose administrations and increasing the frequency to BID. The sponsor may implement alternate administration, such as intermediate doses, alternate dose regimens, or alternate formulations, depending upon PK, PD, and safety results. All BID doses will be taken with water in the morning and evening, approximately 12 hours apart and at least 2 hours after a meal. If possible, subjects should refrain from eating for 1 hour after administration.

See Section [10.2](#) for details regarding the accountability, handling, and disposal of study drug.

Refer to the [INCB053914 IB](#) for additional detail about the respective investigational products.

5.1.3.2. Supply, Packaging, and Labeling

INCB053914 will be provided as 15 mg and 50 mg round, white to off-white tablets packaged in high-density polyethylene bottles. The 15 mg tablets will be smaller than the 50 mg tablets.

No preparation of INCB053914 is required.

CONFIDENTIAL

CONFIDENTIAL

All Incyte investigational product will be labeled with the following statement, "Caution: New Drug—Limited by the United States law to investigational use," or in accordance with local regulatory requirements as applicable.

All Incyte investigational product labels will be in the local language and will comply with the legal requirements of each country.

5.1.3.3. Storage

INCB053914 drug product should be stored according to the conditions stipulated on the investigational product labels.

5.1.3.4. Instructions to Subjects for Handling Study Drug

The subject must be instructed in the handling of study medication as follows:

- To store the study medication according to the conditions listed on the investigational product bottle label.
- To only remove from the study drug bottle(s) the amount of tablets needed at the time of administration.
- Not to remove doses in advance of the next scheduled administration.
- To make every effort to take doses on schedule.
- When taking the study drug at home, take the tablets with a glass of water at least 2 hours after the last meal. It is preferable to refrain from food or drink (other than water) for 1 hour after the dose (unless otherwise advised by the sponsor after completion of food-effect testing).
- To report any missed doses, including any missed injections of cytarabine or azacitidine.
- If the subject vomits after taking study medication, the subject should not take another dose.
- To keep study drug in a safe place and out of reach of children.
- To bring all used and unused study medication bottles and syringes (if applicable) to the site at each visit.
- If a dose of INCB053914 is missed by more than 4 hours, that dose should be skipped, and the next scheduled dose should be administered at the usual time.

5.1.4. Cytarabine

In the Part 3 C-TGA dose-finding cohorts and Part 4 combination expansion 1 (C-TGA E1) cohort, I-DAC will be administered to relapsed/refractory AML subjects as an open-label commercial product at a dose of 1 g/m² per day, 2-hour infusion on Days 1 through 5. A second induction cycle may be started between 15 days and 8 weeks after initiation of Cycle 1, at the discretion of the investigator, in subjects with residual leukemia upon bone marrow assessment during initial induction, provided all drug-related toxic effects had resolved to ≤ Grade 1. Up to 2 additional cycles may be given as consolidation therapy in subjects who achieved CR or

CONFIDENTIAL

CONFIDENTIAL

complete remission with incomplete platelet recovery, at the discretion of the investigator. The start of subsequent induction or consolidation cycles of I-DAC should be coordinated with the Day 1 of the INCB053914 21-day visit cycle when feasible.

If the Part 3 C-TGB dose-finding does not yield a tolerable combination of INCB053914 and azacitidine, or if the Part 4 C-TGB E1 Simon Stage 1 does not yield favorable efficacy data, then the sponsor may elect to evaluate INCB053914 in combination with a L-DAC regimen to treat elderly subjects (≥ 65 years) with newly diagnosed AML (*de novo* or secondary) who are unfit for intensive chemotherapy. In this event, L-DAC will be administered as an open-label commercial product at a dose of 20 mg SC on Days 1 through 10 of a 28- to 42-day cycle, depending upon hematologic recovery. Low-dose cytarabine therapy may continue until Protocol withdrawal criteria are met, or until subject's condition worsens, per investigator's clinical judgment, and warrants withdrawal.

Cytarabine dose modifications for toxicity may be made at the investigator's discretion.

Investigative sites must provide subjects with administration and storage instructions, as per cytarabine package insert or institution standard, for L-DAC SC syringes dispensed to subjects for administration away from the investigative site.

5.1.5. Azacitidine

In the Part 3 C-TGB dose-finding cohorts and Part 4 C-TGB E1 expansion cohort, azacitidine ([Vidaza 2016](#)) will be administered as an open-label commercial product at a dose of 75 mg/m² SC or IV for 7 days during 9-day or less period (ie, a 2-day break allowed on weekend, if needed) of each 28-day treatment cycle. Dose modifications for toxicity will be permitted at the discretion of the investigator.

Azacitidine dose modifications for toxicity may be made at the investigator's discretion.

Investigative sites must provide subjects with administration and storage instructions, as per Vidaza[®] package insert or institution standard, for azacitidine SC syringes dispensed to subjects for administration away from investigative site.

5.1.6. Ruxolitinib

In the Part 3 C-TGC dose-finding cohorts and Part 4 C-TGC E1 expansion cohort, ruxolitinib ([Jakafi 2016](#)) will be administered as an open-label commercial BID oral treatment using the dose designated as the stable dose at the time of the screening visit for each subject. Acceptable doses are 5 mg BID to 25 mg BID.

Doses of ruxolitinib should be self-administered approximately 12 hours apart without regard to food.

Note that subjects must be instructed to withhold the morning dose of ruxolitinib until reaching the clinic for each study visit where administration will occur. The dose may need to be reduced or interrupted for declining platelet count or ANC as described in Section 5.2.4 and will be increased or restarted with recovery of hematologic parameters.

Ruxolitinib should be stored in accordance with the Jakafi[®] package insert.

CONFIDENTIAL

CONFIDENTIAL

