- l. C-TGB Expansion Cohort 1 (C-TGB E1): newly diagnosed AML (*de novo* or secondary) who are ≥ 65 years and unfit to receive intensive chemotherapy. Subjects with acute promyelocytic leukemia are excluded.
- m. C-TGC Expansion Cohort 1 (C-TGC E1): primary or secondary MF who are currently experiencing a suboptimal response on ruxolitinib monotherapy, defined as follows:
 - Palpable spleen of > 10 cm below the left subcostal margin on physical examination at the screening visit OR
 - Palpable splenomegaly of 5 to 10 cm below left subcostal margin on physical exam AND active symptoms of MF at the screening visit as demonstrated by presence of 1 symptom score ≥ 5 or 2 symptom scores ≥ 3 using the Screening Symptom Form ([Appendix O](#)).

3. Parts 1 and 2

- a. Must be unresponsive to currently available therapy, and there is no further SOC therapy available in the judgment of the investigator.
- b. Must not currently be a candidate for curative treatment, including hematopoietic stem cell transplant.

Parts 3 and 4

- c. Subjects with relapsed/refractory AML must have received either induction chemotherapy for AML or hypomethylating agents for hematologic disease before AML.

CONFIDENTIAL

CONFIDENTIAL

- d. Elderly subjects (≥ 65 years) with newly diagnosed AML must be treatment-naive and unfit for intensive chemotherapy.
 - e. Subjects with MF must be receiving ruxolitinib monotherapy at a stable dose for ≥ 8 weeks before Study Day 1. One dose reduction due to toxicities within the 8 weeks before Study Day 1 will be permitted. Acceptable doses are 5 mg BID to 25 mg BID; QD doses are not allowed.
4. Willingness to undergo a pretreatment bone marrow biopsy and/or aspirate (as appropriate to disease), or archival sample obtained since completion of most recent therapy (as appropriate to subjects with existing bone marrow disease or for whom bone marrow examination is a component of disease status assessment). If a biopsy is not possible or contraindicated, or the tissue requirement cannot be satisfied, this requirement may be waived with approval from the medical monitor.
 5. ECOG performance status:
 - a. Part 1: 0 or 1.
 - b. Parts 2 through 4: 0, 1, or 2.
 6. Life expectancy > 12 weeks or ≥ 24 weeks for Part 3 and Part 4 MF subjects.
 7. Willingness to avoid pregnancy or fathering children based on the following criteria:

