3.3. Subject Exclusion Criteria

A subject who meets any of the following criteria will be excluded from the study:

1. Inadequate bone marrow function demonstrated by any of the following:

Laboratory Parameter	TGB (Part 1)	TGB (Part 2)	C-TGC (Parts 3 and 4)
Hemoglobin (g/dL)	< 8.0	< 8.0	Subjects unwilling to receive red blood cell transfusions to treat low hemoglobin levels are excluded.
Platelets ($\times 10^9/L$)	< 75	< 50	< 50 in 2 weeks before screening or platelet transfusions within 4 weeks of screening.
Absolute neutrophils ($\times 10^9/L$)	< 1.0	< 1.0	< 0.5 in the 2 weeks before screening.

Note: No specific hematologic exclusion criteria apply for TGA (Parts 1 and 2), Part 3 C-TGA and C-TGB, and Part 4 C-TGA E1 and C-TGB E1 cohorts.

CONFIDENTIAL

CONFIDENTIAL

2. Inadequate organ function demonstrated by any of the following, unless approved by the medical monitor:
 - Part 1 and Part 3
 - a. Total bilirubin > upper limit of normal (ULN; except total bilirubin > ULN is acceptable if direct bilirubin is $\leq 1.2 \times$ ULN. Subjects with Gilbert's syndrome who have total bilirubin $\leq 2 \times$ ULN may be enrolled with medical monitor approval).
 - b. AST or ALT > $1.5 \times$ ULN.
 - c. Creatinine clearance < 50 mL/min (< 30 mL/min for MM) based on Cockcroft-Gault formula or 24-hour urine analysis.
 - Part 2 and Part 4
 - d. Total bilirubin > ULN (except total bilirubin > ULN is acceptable if direct bilirubin is $\leq 1.2 \times$ ULN. Subjects with Gilbert's syndrome who have total bilirubin $\leq 2 \times$ ULN may be enrolled with medical monitor approval).
 - e. AST or ALT > $1.5 \times$ ULN.
 - f. Creatinine clearance < 40 mL/min (< 30 mL/min for MM) based on Cockcroft-Gault formula or 24-hour urine analysis.
3. Receipt of anticancer medications or investigational drugs within the following interval before the first administration of study drug (note: subjects enrolling in C-TGC must continue to receive their ruxolitinib throughout the study):
 - a. < 5 half-lives or 14 days, whichever is longer, for any investigational agent.
 - b. < 28 days for any antibodies or biological therapies.
 - c. < 5 half-lives for all other nonbiologic anticancer medications, or sponsor approval.
 - d. < 6 weeks for mitomycin-C or nitrosoureas.

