^h If screening serum pregnancy testing is performed within 7 days of treatment initiation, it does not need to be repeated at Cycle 1 Day 1.

ⁱ Cycle 1 only. See Table 14 for sample collection details. The visit window for the D8 PK sample (± 2 days) should be applied to collect samples on a cycle day when both azacitidine and INCB053914 are given.

CONFIDENTIAL

CONFIDENTIAL

Table 14: Pharmacokinetic Assessments for Azacitidine Combination Cohorts

Visit	Assessment	Fasting Requirement	HOLD AM Dose	Predose	INCB053914 Dose	Azacitidine Dose	Time Postdose				
							1 h ± 15 min		2 h ± 15 min	4 h ± 15 min	8 h ± 30 min
C1D8 ^a	PK plasma	Fast overnight	X	X	♦ ^b	♦	X	Snack/meal	X	X	X
C1D15	PK plasma	Fast overnight	X	X	♦	n/a	X	Snack/meal	X	X	X

^a Use the ± 2-day window to ensure that these samples are collected on a day when both INCB053914 and azacitidine are administered.

^b INCB053914 dose should be administered just before the daily dose of azacitidine.

CONFIDENTIAL

CONFIDENTIAL

Table 15: Schedule of Assessments for Ruxolitinib Combination Cohorts

Visit Day (Range)	Section	Screening	Treatment Phase ^a							EOT	Follow-up Phase	
		Day -28 to Day -1	Day 1	Weeks 1, 2, 3 ^b	Weeks 4, 8 ± 5 Days	Week 12 ± 5 Days	Weeks 16, 20 ± 5 Days	Week 24 ± 5 Days	Extension Visits (Q12W After Week 24) ± 7 Days	+3 Days	Safety Follow-Up + 30-35 Days After EOT	Survival Follow-Up Every 12 Weeks
Informed consent	7.1	X										
Inclusion/exclusion criteria	3	X	X									
Contact IRT	7.2	X	X		X	X	X	X	X	X		
Medical and cancer history	7.3.1	X										
Prior/concomitant medication	7.4	X	X	X	X	X	X	X	X	X	X	
Transfusion history/status	7.3.2	X	X		X	X	X	X	X	X	X	
Screening Symptom Form	7.3.3	X										
Administer INCB053914 in clinic	Table 17		X	X	X	X	X	X				
Administer ruxolitinib in clinic	Table 17		X	X	X	X	X	X	X			
Drug dispense/compliance check	5.1.7		X		X	X	X	X	X	X ^c		
Comprehensive physical examination	7.5.2.1	X						X		X	X	
Targeted physical examination	7.5.2.2		X	X	X	X	X		X	X		
ECOG performance status	7.7.1	X	X		X	X	X	X	X	X	X	
Vital signs/height/weight ^d	7.5.3	X ^d	X		X	X	X	X	X	X	X	
12-lead ECG	7.5.4	X	X					X		X	X	
AE assessment ^e	7.5.1	X	X	X	X	X	X	X	X	X	X	
Laboratory assessments	Table 16	X	X	X	X	X	X	X	X	X	X	
Buccal swab	7.9.2	X										
Provide reminder card	7.10.1	X	X	X	X	X	X	X	X	X		

CT = computed tomography; ECG = electrocardiogram; MRI = magnetic resonance imaging, PGIC = Patient Global Impression of Change.

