^a See Table 16 for scheduled visits where only lab assessments are collected (lab-only visits).

^b Week 1 and Week 3 visits only pertain to Part 3 subjects.

^c Compliance check only.

CONFIDENTIAL

CONFIDENTIAL

^d Height is only assessed at screening.

^e Subjects must be followed for AEs for 30 days (+ 5 days) after the EOT visit (or after the last dose of study drug if the EOT visit was not performed).

CONFIDENTIAL

CONFIDENTIAL

Table 16: Laboratory Assessments for Ruxolitinib Combination Cohorts

Visit	Section	Screening	Day 1	Weeks 1, 3 Part 3 ONLY	Weeks 2, 6, 10, 14, 18, 22, then Q4W	Weeks 4, 8, 12, 16, 20, 24, then Q12W	EOT	Follow-Up 30-35 Days After Last Dose of INCB053914
Evaluation/Window				The window for laboratory visits is ± 3 days				
Overnight fast before assessments	Table 17		X		X ^a	X ^a		
Comprehensive blood chemistries	Table 21	X ^b	X ^b	X		X	X	X
Hematology with differential	Table 21	X ^b	X ^b	X	X	X	X	X
LFT panel ^c	Table 21	X ^b	X ^b	X	X	X	X	X
Coagulation panel ^c	Table 21	X ^b	X ^b	X		X	X	X
Urinalysis	Table 21	X				X ^d	X	X
Lipid panel (requires overnight fast)	Table 21	X				X ^d	X	X
Hepatitis screening	Table 21	X						
Serum pregnancy	7.5.5.2	X	X ^e					X
PK – plasma	7.8.1		X		X ^f	X ^f		

^a At Week 2 and Week 4 only.

^b Blood chemistry (including LFTs) and hematology screening assessments used to determine eligibility must be collected within 14 days before Cycle 1 Day 1. Cycle 1 Day 1 blood chemistry, hematology, LFT panel, and coagulation panel assessments may be omitted if the screening assessments were performed within 3 days before Cycle 1 Day 1.

^c Additional LFT and coagulation monitoring may be required as per Table 5 and Appendix S

^d Required Weeks 12 and 24 and Q12W.

^e If screening serum pregnancy testing is performed within 7 days of treatment initiation, it does not need to be repeated at Cycle 1 Day 1.

^f Pharmacokinetic sampling will occur on Day 1, Week 2, and Week 4 only. See Table 17.

CONFIDENTIAL

CONFIDENTIAL

Table 17: Pharmacokinetic Assessments for Ruxolitinib Combination Cohorts

Visit	Assessment	Fasting Requirement	HOLD AM Doses	Predose	Drug Administration	Time Postdose			Drug Administration	
						1 h ± 15 min	2 h ± 15 min	4 h ± 15 min		
Day 1	PK plasma	Fast overnight	N/A	X	Ruxolitinib	X	Snack/meal	X	X	INCB053914
Week 2	PK plasma	Fast overnight	X	X	INCB053914	X	Snack/meal	X	X	Ruxolitinib
Week 4	PK plasma	Fast overnight	X	X	INCB053914 + Ruxolitinib	X	Snack/meal	X	X	N/A

CONFIDENTIAL

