7.10.2. Distribution of Subject Reminder Cards

Subjects will be provided with subject reminder cards at each visit. The subject reminder cards will indicate the date and time of the next visit. The reminder cards will have a field for the subject to enter the date and time of the last dose taken before the visit and to record the time of the last meal before applicable visits as per [Table 8](#), [Table 11](#), [Table 14](#), [Table 17](#), and [Table 20](#). Reminder cards will include instructions specific for the study visits, including for visits where the subject will refrain from taking the study drug at home in the morning before the clinic visit. All necessary instructions, such as those for study drug administration, concomitant medications, and laboratory tests should be provided to the subject in writing on this reminder card or on accompanying written materials.

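### Table 17 marks the hold on home morning doses N/A for Day 1 of the ruxolitinib cohorts, in conflict with Protocol Section 5.1.6 and Table 15

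*Protocol*

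**What the plan says.** Protocol Section 5.1.6 (Ruxolitinib) requires that "subjects must be instructed to withhold the morning dose of ruxolitinib until reaching the clinic for each study visit where administration will occur". It makes no exception for Day 1.

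Table 15 (schedule of assessments for the ruxolitinib cohorts) has a row "Administer ruxolitinib in clinic". It is blank at screening, marked from Day 1 onward, and refers the reader to Table 17.

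Table 17 (PK assessments for the same cohorts) has a column for holding the morning doses, followed by a predose sample column. Its Day 1 row reads "Day 1 PK plasma Fast overnight N/A X Ruxolitinib". Samples follow at 1, 2 and 4 hours, and INCB053914 is then given. The later rows read "Week 2 PK plasma Fast overnight X X INCB053914" and "Week 4 PK plasma Fast overnight X X INCB053914 + Ruxolitinib"; the first X in each is the hold entry.

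On prior treatment, inclusion criterion 3e in Section 3.2 says "Subjects with MF must be receiving ruxolitinib monotherapy at a stable dose for ≥ 8 weeks before Study Day 1", at 5 to 25 mg BID. Exclusion criterion 3 in Section 3.3 notes that "subjects enrolling in C-TGC must continue to receive their ruxolitinib throughout the study".

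Section 7.10.2 says "Reminder cards will include instructions specific for the study visits", including visits where the study drug is not taken at home that morning. It cites Table 17 among the tables for recording last dose and last meal. SAP Section 5.3.4 has the study pharmacokineticist review drug administration and sample records to identify subjects to exclude from PK analyses.

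**The concern.** Two parts of one protocol give different messages about the same morning. Section 5.1.6 covers every visit with in-clinic ruxolitinib, and Table 15 makes Day 1 one of them. The operational table to which Table 15 sends the site says, for that day, that holding does not apply.

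The subject arrives on an established twice-daily drug, so a home morning dose is due. If the site prepares the visit or the reminder card from Table 17 alone, the subject may take that dose and then be dosed again in the clinic. Two things are then at stake. One is an unplanned repeat of the morning ruxolitinib dose. The other is the Day 1 sampling: the sample labelled predose would follow a dose taken that morning, and the 1, 2 and 4 hour samples would reflect two doses.

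**Working it through.** No sample size, power or alpha figure is involved. The check sets the entries side by side and then counts doses.

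**Step 1: the three rows of Table 17.**

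| Visit | Hold morning doses | Predose sample | Given first | Samples | Given after last sample |
|---|---|---|---|---|---|
| Day 1 | N/A | X | Ruxolitinib | 1, 2, 4 h | INCB053914 |
| Week 2 | X | X | INCB053914 | 1, 2, 4 h | Ruxolitinib |
| Week 4 | X | X | Both | 1, 2, 4 h | N/A |

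**Step 2: which drug can N/A describe?** On Day 1 INCB053914 has never been taken, so there is no home dose of it to hold. Ruxolitinib has been taken at a stable dose for at least 8 weeks and is not stopped at entry, so a home dose does exist. The column heading in Table 17 refers to doses in the plural, whereas the corresponding column in Tables 8, 11, 14 and 20 uses the singular. The natural reading is therefore that the cell covers both drugs.

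**Step 3: likely source.** Monotherapy Table 8 has the same entry at Cycle 1 Day 1, where it fits, because no study drug precedes that visit. The layout was probably carried over. SAP Section 4.1.1 shows a similar assumption: it defines Day 1 of combination therapy as the first dose of any study drug and lists ruxolitinib among them.

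**Step 4: dose count if the home dose is taken.** Let d be the subject's stable dose, 5 to 25 mg.
- Planned daily total: 2 × d = 10 to 50 mg.
- Home, clinic and evening doses: 3 × d = 15 to 75 mg.
- Excess: 3d − 2d = d = 5 to 25 mg, on one day.

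**Step 5: what the Day 1 samples can show.** INCB053914 is given only after the 4 hour sample, so no Day 1 sample can contain it. Those samples can inform only on ruxolitinib. The order of visits (ruxolitinib first on Day 1, INCB053914 first at Week 2, both at Week 4) suggests that Day 1 is a ruxolitinib-alone profile. This is an inference. The visible PK endpoints and analyses (Protocol Sections 2.2.2 and 9.4.5; SAP Sections 2.3.2 and 8) name INCB053914 only, and parts of the objectives and endpoints are redacted.

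**The case against.** The strongest reply is that an explicit instruction already exists. Section 5.1.6 is mandatory and unqualified, Table 15 agrees with it, and the Day 1 row of Table 17 itself calls for a predose sample. N/A is not an instruction to take the dose at home. Reminder cards are issued from screening and have a field for the last dose before the visit, Section 7.8.1 requires the last-dose time with each PK sample, and SAP Section 5.3.4 provides a review that can exclude affected data.

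Most of this stands, and it limits the point to a risk. It does not remove the conflict. The overnight fast is no safeguard, since Section 5.1.6 allows ruxolitinib without regard to food. Sections 7.8.1 and 7.10.2 speak of study drug, so it is not certain that the last-dose record or the card covers ruxolitinib.

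A reader might infer three stronger things that the documents do not support:
- **That every C-TGC subject would be affected.** The planned numbers (about 3 to 10 in Part 3 and up to 16 in C-TGC E1) are a ceiling. It would be reached only if every site followed the cell over Section 5.1.6 and every subject took the home dose.
- **That a planned Day 1 versus Week 4 ruxolitinib comparison is lost or biased.** No such comparison appears in the visible text. If one exists, an inflated Day 1 profile would make Week 4 ruxolitinib exposure look lower, but that is conditional.
- **That one extra dose would cause cytopenia.** Section 1.4.3.3 calls ruxolitinib thrombocytopenia dose-dependent, but nothing in the documents addresses a single additional dose.

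**Conclusion.** The Day 1 hold entry in Table 17 conflicts with Section 5.1.6 and Table 15, and the passages must be reconciled. This is an internal inconsistency in an operational table, not a flaw in the trial's design. For a subject whose site relied on Table 17 alone, the possible consequence is one repeated morning dose (5 to 25 mg) on one day and a predose sample that does not precede the morning's dosing. How often this would happen cannot be estimated from the documents.

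The conclusion on dosing rests only on the stated entry criteria and tables. The conclusion on PK rests on the further assumption that the Day 1 samples are meant as a ruxolitinib-alone profile. If so, a spoiled profile could not be repeated once INCB053914 starts.

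**What to change.** - Reconcile the Day 1 cell of Table 17 with Section 5.1.6, and show the hold entry separately for INCB053914 and ruxolitinib. Which instruction applies is for the sponsor to settle; the need is for a single one.
- Carry that reconciled instruction onto the reminder card issued at screening, naming ruxolitinib so that the wording does not depend on how study drug is read.
- Within the existing review in SAP Section 5.3.4, check the recorded last ruxolitinib dose time for each Day 1 profile and flag any with a home dose that morning. Confirm that the last-dose record in Section 7.8.1 captures ruxolitinib.

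The cost is one table cell and its column layout, a line of card text, and one added check in a review already planned. No visit, sample or procedure is added.
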